12.1.7 Tabulation of the Per Protocol Populations

Per product use period, there will be one per protocol population. In the tables per period on the PP population, each period will show its corresponding PP population, and the baseline will be repeated per PP population. As for a repeated measurements model, each period will include its own PP population and the value for any subject in the PP of that period would be used. In the tables that are not by period, the table will be repeated for each PP population.

12.1.8 Multiple Comparisons / Multiplicity

Unless stated otherwise, all statistical tests will be conducted using a one-sided test with 2.5% type I error probability, and all quoted confidence intervals (CIs) will be two-sided 95% CIs.

The primary endpoints will be tested using a closed testing procedure to preserve the overall alpha level by simultaneously testing the endpoints at the one-sided 2.5% type I error probability (**EMEA Points to consider on multiplicity issues in clinical trials**). This implies that statistical significance is required for all primary endpoints in order to be able to make confirmatory claims about any of the endpoints.

No adjustment for multiplicity will be made on any of the secondary endpoints.

12.2 Disposition of Subjects

The number and percent of subjects will be summarized for the following categories: subjects screened, enrolled subjects, exposed and not randomized, randomized subjects, completed confinement, period 2, 3 and 4 and safety follow-up, and discontinued (if applicable discontinued subject that never used their allocated products will be identified) (Table 15.2.1.1).

All subjects who screenfail or discontinue the study will be categorized by their primary reason for screen failure or discontinuation. Disposition of subjects and reasons for screen failure / discontinuation will also be summarized separately (Table 15.2.1.2.1 and Table 15.2.1.2.2). Supportive listings will be provided (Listing 15.3.1.7).

The number and percent of randomized subjects with protocol deviations and the number of protocol deviations will be summarized by arm, broken down by main deviation category (major/minor) sub-categories and evaluability (Table 15.2.1.3.1). Subjects will be counted once per deviation category and per product use period, and can be counted for more than one deviation category. The number and percent of randomized subjects per study analysis population and reasons for exclusion will be summarized by arm (Table 15.2.1.3.2).

Supportive listings will be provided, including any additional comments for tests that are not performed to be included on the listings of individual data (Listing 15.3.1.10).

12.3 Demographics and Other Baseline Characteristics

Demographic and baseline characteristics will be summarized for the Safety Population, FAS and PP for period 1 and 4 (Table 15.2.1.4.1, Table 15.2.1.4.2 and Table 15.2.1.4.3 respectively), and listed for all screened subjects (Listing 15.3.1.6).

The demographic variables age, sex, race, waist circumference, body weight, height and BMI, CC Nicotine level at Admission (mg), CC ISO CO level at Admission (mg), and CC ISO tar level at Admission (mg) will be summarized by exposure, and by sex, CC consumption and Product use category (Table 15.2.1.4.2.X and Table 15.2.1.4.3.X).

No inferential analyses will be presented for the demographic and baseline characteristics.

12.3.1 Socio-Economic Status (SES)

SES data will be listed as part of the demographics and baseline characteristics (Section 12.3) (Listing 15.3.1.9).

12.3.2 Current Cigarette Brand and Smoking Characteristics

The following smoking characteristics at Admission (Day -3) will be summarized and listed as specified in Section 12.3. ISO tar yields (continuous and categorized as 1-5 mg, 6-8 mg, 9-10 mg and > 10 mg), ISO nicotine level (continuous and categorized as ≤ 0.6 mg and > 0.6 to ≤ 1 mg), ISO CO level (continuous), and number of CCs smoked on a daily basis during the previous 6 weeks and since the subject started smoking (continuous and categorized as 10-19 CC/day and >19 CC/day).

Current CC brand(s) smoked by the subject and recorded at Screening and Admission (Day -3) will be summarized (Table 15.2.1.5) and listed by arm for the FAS. This will include brand name(s) and ISO nicotine, tar, and CO yields. Data at screening will be listed only (Listing 15.3.1.2).

Smoking habits/history, including whether subjects have smoked for at least the last ten years, number of years smoked, how many cigarettes per day the subject has smoked over the last 6 weeks (and how much were non-menthol) and since the subject started smoking; whether the subject ever used nicotine-containing products other than commercially available non-menthol/menthol CC; and the average use of e-cigarettes over the last year, and product preference will be listed by product at Screening and Admission (Day -3) where applicable (Listing 15.3.1.3 and Listing 15.3.1.4).

12.3.3 Medical History and Concomitant Diseases

Medical history is defined as any condition that started and ended prior to Screening. Medical history will be coded using MedDRA version 18.0 and listed separately by arm, System Organ Class (SOC) and Preferred Term (PT) within SOC (Listing 15.3.1.8).

Medical History will be summarized by arm, SOC and PT for the Safety Population (Table 15.2.1.6).

Concomitant disease is defined as any condition diagnosed at Screening or was ongoing at Screening. Concomitant disease will be coded using MedDRA version 18.0 and listed separately by arm, SOC and PT within SOC (Listing 15.3.1.8).

Concomitant disease will be summarized by arm, SOC and PT for the Safety Population (Table 15.2.1.7).

Partial dates will not be imputed, but assumptions will be made as follows to assign to either medical history or concomitant diseases (see section **12.1.5 Handling of Dropouts or Missing Data (including outside the limits of quantification)**).

12.3.4 Other Data

Other data collected at Screening and/or Admission will be listed by arm (Listing 15.3.1.5, Listing 15.3.6.6 and Listing 15.3.1.4). These data are as follows:

- Cotinine urine test
- Serum and Urine pregnancy test
- Chest x-ray
- Urine drug screen
- Serology
- Alcohol breath test
- Prior and concomitant medication
- Willingness to use CHTP 1.2

12.4 Extent of Exposure (Product Consumption)

Details of the product test and of daily product use will be listed and summarized (Table 15.2.2.X and Listing 15.3.2.1). For the FAS, the summaries will be repeated per Product Use Category for the ambulatory period and per Product Preference for the confinement and ambulatory period (Table 15.2.2.3.X):

- The number of uses of CHTP 1.2 at product test will be tabulated per arm.
- During the confinement period: descriptive statistics of the number of uses on a day-by-day basis per product.
- During the ambulatory period: descriptive statistics per product period of the average and the maximum daily usage per product.

12.5 Planned Statistical Analyses

12.5.1 Primary Analyses

The per-protocol population for period 1 and period 4 will be the primary analysis set for biomarkers of exposure. See also **section 12.1.7**.

12.5.1.1 Primary endpoints

COHb in blood, and urinary concentrations adjusted for creatinine of MHBMA, 3-HPMA and S-PMA, and total NNAL will be summarized on the log-scale as detailed in **Section 12.1.3 “Descriptive Statistics”**. Distributions will be tested for log-normality and appropriate non-parametric methods will be used in case of non-lognormally distributed data as described in **12.1 General Considerations**.

The values and percent changes from baseline in the concentration adjusted for creatinine of MHBMA, 3-HPMA, S-PMA and total NNAL will be listed and summarized along with the COHb concentrations and percent changes from baseline (Tables 15.2.3.3-7.1, 15.2.3.3-7.2 and Listing 15.3.3.1). This will also be summarized by sex, by average cigarette consumption over the previous 6 weeks prior to admission and by product use category (Tables 15.2.3.3-7.1.1, 15.2.3.3-7.1.2 and 15.2.3.3-7.1.3).

The log-transformed data will be analyzed by means of an ANCOVA (on Day 5 for COHb, MHBMA, 3-HPMA and S-PMA and Day 90 Visit for total NNAL) using arm as covariate adjusting for sex and average cigarette consumption over the previous 6 weeks prior to admission, and log-transformed baseline value of endpoint.

The SAS code to be used for COHb in blood, and urinary concentrations adjusted for creatinine of MHBMA, 3-HPMA and S-PMA on Day 5 and total NNAL adjusted for creatinine at Day 90 Visit is shown below:

```
Proc mixed data=_data_ ;  
Class arm sex cigarette_cons ;  
Model log (Value) = log (baseline) sex cigarette_cons arm ;  
Lsmeans arm / pdiff =control('CC') alpha=0.05 cl ;  
Run ;
```

The least squares (LS) means and estimate of the difference along with its 95% CI will be back-transformed before presenting in the tables. The geometric LS means for each arm along with the reduction (i.e: 100% - ratio of CHTP 1.2 : CC (%)) and 95% CI will be presented in the tables (Table 15.2.3.1).

In addition line graphs will be produced for arm geometric means (and 95% CI) over all timepoints for COHb in blood, and urinary concentrations adjusted for creatinine of MHBMA, 3-HPMA, S-PMA and total NNAL (Figure 15.1.1.1-5).

The listing of the urinary biomarkers will include the concentration, the percent change in the concentration, the concentration adjusted for creatinine, the percent change in the concentration adjusted for creatinine, the volume of urine in the 24 hour collection, the quantity excreted over 24 hours, the percent change in quantity excreted over 24 hours and the values for creatinine for the 24h urine (Listing 15.3.3.1).

The listing of the COHb data will include the concentration, the percent change in the concentration, and a flag for whether a subject's COHb is <2% (Listing 15.3.3.1).

If applicable, the tables with descriptive statistics will be repeated for the group of subjects who attempt to quit (see section “**10.7 Quitters Population**”)

12.5.1.2 Confirmatory Hypothesis

The hypothesis to be tested for each of the biomarkers of exposure of the primary objectives is that the geometric mean level on Day 5 for COHb, MHBMA, 3-HPMA and S-PMA and at Day 90 Visit for total NNAL for CHTP 1.2 is lower relative to CC.

Analysis of BoExp will be conducted on the natural log scale in order to test the following hypothesis:

- Null hypothesis (H_0): $m_1 \geq m_2$
- Alternative hypothesis (H_1): $m_1 < m_2$

Where m_1 and m_2 are the geometric means of COHb, MHBMA, 3-HPMA and S-PMA levels on Day 5 and total NNAL levels at Day 90 Visit for CHTP 1.2 and CC respectively.

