Abbreviations: Total NNAL = Total 4-(methylnitrosamino)-1-(3-pyridyl)-1-butanol; MR = Mean ratio; CHTP 1.2 = Carbon Heated Tobacco Product 1.2; CC = Combustible cigarettes; CV = Coefficient of variation.

The power to detect a reduction was computed.

Table 22 describes the expected power to detect a reduction of 50% or more in the levels of MHBMA, 3-HPMA, S-PMA, and COHb in CHTP 1.2 arm compared to the CC arm after 5 days of exposure and total NNAL after 90 days of exposure, with a one sided test with 2.5% type I error probability using the assumptions from YVD-CS01-EU and, and 120 randomized subjects in a 2:1 ratio (80 in CHTP 1.2 arm and 40 in CC arm). It is assumed that a minimal number of subjects will be excluded from the PP set in confinement for both arms and CC in ambulatory, whereas at least 50% will remain in the PP set in ambulatory for CHTP 1.2, therefore a 2:1 randomization ratio was chosen.

Confidentiality Statement

Data and information contained in this document are considered to constitute trade secrets and confidential commercial information, and the legal protections provided to such trade secrets and confidential information are hereby claimed under the provisions of applicable law. No part of this document may be publicly disclosed without the written consent of Philip Morris Products S.A.

Table 22 Expected Power

Assumptions	Reduction					
	50%	51%	52%	53%	54%	55%
YVD-CS01-EU	94%	88%	81%	70%	56%	38%

The test-wise powers to detect a reduction of 50% or more in the levels of MHBMA, 3-HPMA, S-PMA, and COHb on Day 5 and in total NNAL after 90 days in smokers switching from CC to the CHTP 1.2 as compared to smokers continuing to use CC, using a one-sided test with 2.5% type I error probability using the assumptions from YVD-CS01-EU, and 120 randomized subjects in a 2:1 ratio (80 in CHTP 1.2 arm and 40 in CC arm) are described in [Table 23](#).

Table 23 Test-Wise Power

Parameter	Test-Wise Power
COHb	96%
3-HPMA	>99%
MHBMA	>99%
S-PMA	>99%
Total NNAL	98%

Given the above calculation, the sample size was considered sufficient to have more than 80% power to detect a reduction of 50% or more in the levels of MHBMA, 3-HPMA, S-PMA, and COHb in CHTP 1.2 arm compared to the CC arm after 5 days of exposure, and in the levels of total NNAL in the CHTP 1.2 arm compared to the CC arm after 90 days of exposure, using a one sided test with 2.5% type I error probability.

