12.4.4 Confirmatory Analyses

The hypothesis to be tested for each of the BoExp of the primary and secondary objectives that the geometric mean level on Day 5 of the BoExp (MHBMA; 3-HPMA; S-PMA; COHb) and at Visit 4 of the BoExp total NNAL, respectively, for CHTP 1.2 is lower relative to CC.

Analysis of BoExp will be conducted on the natural log scale. In order to test the following hypothesis:

- Null hypothesis (H_0): $m_1 \geq m_2$
- Alternative hypothesis (H_1): $m_1 < m_2$

Where m_1 and m_2 are the geometric means of the BoExp levels on Day 5 and at Visit 4, respectively, for CHTP 1.2 and CC respectively.

The transformed data will be analyzed by means of a generalized linear model using product arm as covariate adjusting for the following Baseline information: gender, average cigarette consumption over the previous 6 weeks, and Baseline value of endpoint. Estimates of differences between groups will be back-transformed to provide relative effects.

Assumptions of the analysis of variance model will be tested. Markedly non-lognormally distributed BoExp data will be transformed or analyzed by appropriate non-parametric methods.

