5.4.2 Evaluation Criteria

The study is designed to be able to detect a reduction of 50% or more in the levels of MHBMA, 3-HPMA, S-PMA, and COHb after 5 days of exposure, and in total NNAL after 90 days of exposure in smokers switching from CC to the CHTP 1.2 as compared to smokers continuing to use CC, using a one-sided test with 2.5% type I error probability.

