**Table 9 Expected Mean Ratios and Coefficients of Variation for CHTP 1.2/CC after 90 Days of exposure**

	CHTP 1.2/CC MR (CV)
Total NNAL	0.30 (0.60)

Abbreviations: Total NNAL = Total 4-(methylnitrosamino)-1-(3-pyridyl)-1-butanol; MR = Mean ratio; CHTP 1.2 = Carbon Heated Tobacco Product 1.2; CC = Combustible cigarettes; CV = Coefficient of variation.

The power to detect a reduction was computed and is presented below.

Table 10 describes the expected power to detect a reduction of 50% or more in the levels of MHBMA, 3-HPMA, S-PMA, and COHb in CHTP 1.2 arm compared to the CC arm after 5 days of exposure and total NNAL after 90 days of exposure, with a one sided test with 2.5% type I error probability using the assumptions from YVD-CS01-EU and, and 120 randomized subjects in a 2:1 ratio (80 in CHTP 1.2 arm and 40 in CC arm). It is assumed that a minimal number of subjects will be excluded from the PP set in confinement for both arms and CC in ambulatory, whereas at least 50% will remain in the PP set in ambulatory for CHTP 1.2, therefore a 2:1 randomization ratio was chosen.

Table 10 Expected Power

Assumptions	Reduction					
	50%	51%	52%	53%	54%	55%
YVD-CS01-EU	94%	88%	81%	70%	56%	38%

The test-wise powers to detect a reduction of 50% or more in the levels of MHBMA, 3-HPMA, S-PMA, and COHb on Day 5 and in total NNAL after 90 days in smokers switching from CC to the CHTP 1.2 as compared to smokers continuing to use CC, using a one-sided test with 2.5% type I error probability using the assumptions from YVD-CS01-EU, and 120 randomized subjects in a 2:1 ratio (80 in CHTP 1.2 arm and 40 in CC arm) are described in **Table 11**.

Table 11 Test-Wise Power

Parameter	Test-Wise Power
COHb	96%
3-HPMA	>99%
MHBMA	>99%
S-PMA	>99%

Total NNAL 98%

Given the above calculation, the sample size was considered sufficient to have more than 80% power to detect a reduction of 50% or more in the levels of MHBMA, 3-HPMA, S-PMA, and COHb in CHTP 1.2 arm compared to the CC arm after 5 days of exposure, and in the levels of total NNAL in the CHTP 1.2 arm compared to the CC arm after 90 days of exposure, using a one sided test with 2.5% type I error probability.

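### The confirmatory test asks for any reduction, but the evaluation criterion and every stated power figure are for a reduction of at least 50%

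*SAP*

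**What the plan says.** **The test.** Protocol 12.4.4 and SAP 12.5.1.2 set H0: m1 ≥ m2 against H1: m1 < m2, where m1 and m2 are the geometric means for CHTP 1.2 and CC. In words, the Protocol's hypothesis is that the level "for CHTP 1.2 is lower relative to CC"; the SAP's is that the geometric mean, on Day 5 for the other four biomarkers and "at Day 90 Visit for total NNAL for CHTP 1.2 is lower relative to CC". The SAS code in SAP 12.5.1.1 estimates the arm difference on the log scale with no offset, so the comparison is with a ratio of 1. Protocol 12.1.5 and SAP 12.1.8 require one-sided significance at 2.5% on all five primary endpoints before any confirmatory claim.

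**The criterion.** Protocol 12.4.1 and SAP 5.4.2, under the label of evaluation criterion, say: "The study is designed to be able to detect a reduction of 50% or more in the levels of MHBMA, 3-HPMA, S-PMA, and COHb" (Day 5), and likewise for total NNAL after 90 days, with the same one-sided 2.5% test.

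**The power.** Protocol 12.2 introduces Table 23 with "The test-wise powers to detect a reduction of 50% or more in the levels of MHBMA, 3-HPMA, S-PMA, and COHb on Day 5", and SAP 8 concludes that "the sample size was considered sufficient to have more than 80% power to detect a reduction of 50% or more". Protocol Table 22 (SAP Table 10) gives joint power of 94, 88, 81, 70, 56 and 38% for reductions of 50, 51, 52, 53, 54 and 55%. Protocol Table 23 (SAP Table 11) gives 96% for COHb, 98% for total NNAL and above 99% for the other three.

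SAP 9, which lists departures from the protocol, does not mention the 50% figure.

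**The concern.** The criterion and the sizing refer to a 50% reduction; the hypothesis refers to no reduction. If the 50% belongs in the null, the written test is much easier to pass than the one the trial was sized for, and the quoted powers describe a test that nobody will run. The trial could then report confirmatory success on all five endpoints when some or all of the reductions fall well short of 50%, and no rule in either document would prevent that result being presented against the stated criterion.

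**Working it through.** **Inputs.** Planning mean ratios and CVs are from Protocol Tables 20 and 21 (SAP Tables 8 and 9). Group sizes are 80 and 40 on Day 5. For total NNAL they are 40 and 40, because Protocol 12.2 assumes that at least 50% of the CHTP 1.2 arm stays in the ambulatory per-protocol set, with minimal loss in the CC arm. Alpha is 0.025 one-sided.

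**Method.** SD on the log scale = √ln(1 + CV²); SE = SD × √(1/n1 + 1/n2). Power is from the noncentral t distribution with noncentrality ln(margin/MR)/SE, where the margin is the ratio in the null. For COHb, SD = √ln(1 + 0.32²) = 0.3122 and SE = 0.3122 × √(1/80 + 1/40) = 0.0605. For total NNAL, SD = √ln(1 + 0.60²) = 0.5545 and SE = 0.5545 × √(2/40) = 0.1240.

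**Step 1: reproduce test-wise power with the margin at 0.50.** Noncentrality is ln(0.50/0.40)/0.0605 = 3.69 for COHb and ln(0.50/0.30)/0.1240 = 4.12 for total NNAL.

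| Endpoint | MR (CV) | Power, margin 0.50 | Stated | Power, margin 1 (as written) |
|---|---|---|---|---|
| COHb | 0.40 (0.32) | 95.5% | 96% | >99.99% |
| 3-HPMA | 0.30 (0.50) | >99.9% | >99% | >99.99% |
| MHBMA | 0.15 (0.70) | >99.9% | >99% | >99.99% |
| S-PMA | 0.20 (0.70) | >99.9% | >99% | >99.99% |
| Total NNAL | 0.30 (0.60) | 98.3% | 98% | >99.99% |

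**Step 2: reproduce joint power, using each column of Table 22 as the margin.** Two ways of combining the five tests are shown: the lower bound 1 − Σ(1 − power), and the product, which assumes independence.

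| Required reduction | 50% | 51% | 52% | 53% | 54% | 55% |
|---|---|---|---|---|---|---|
| Stated | 94% | 88% | 81% | 70% | 56% | 38% |
| Lower bound | 93.8% | 88.8% | 81.1% | 69.9% | 55.2% | 37.9% |
| Product | 93.9% | 89.1% | 81.6% | 71.2% | 58.1% | 43.6% |

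The lower bound agrees with all six stated values to within one point. The direction alone is decisive: stated power falls as the reduction rises, which happens only if the reduction is the hurdle in the null. If the columns were true reductions tested against no reduction, joint power would be about 99.96% at 50% and would rise from there.

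**Step 3: what each test requires of the data.** The largest significant observed ratio is margin × exp(−t × SE), with t = 1.980 (118 df) on Day 5 and 1.991 (78 df) for total NNAL.

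| Endpoint | SE | As written: ratio (reduction) | Margin 0.50: ratio (reduction) |
|---|---|---|---|
| COHb | 0.0605 | 0.89 (11%) | 0.44 (56%) |
| 3-HPMA | 0.0915 | 0.83 (17%) | 0.42 (58%) |
| MHBMA, S-PMA | 0.1223 | 0.78 (22%) | 0.39 (61%) |
| Total NNAL | 0.1240 | 0.78 (22%) | 0.39 (61%) |

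**Step 4: chance of success when the criterion is missed.** If every true reduction were 30%, the written test has power above 99.9% (COHb), 97% (3-HPMA), 82% (MHBMA and S-PMA) and 81% (total NNAL). The product is about 54%. The same calculation gives about 5% if every true reduction is 20%, and 0.5% if 15%.

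**The case against.** The best defence is that the plan is coherent without the 50%. The primary objectives speak of demonstrating a reduction and give no size; the hypothesis, model and multiplicity rule all match that. On this reading the evaluation criterion is a statement of sensitivity, and sizing for a harder target only adds spare power. Type I error against the written null is not inflated. The reduction and its 95% CI will appear in Table 15.2.3.1, so a reader can check 50% directly.

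Some of this stands. The trial is not underpowered, the estimates are unaffected, and if the planning ratios of 0.15 to 0.40 hold, both tests will probably succeed. All five endpoints must pass, so joint success with true reductions as small as 11 to 22% is unlikely; the realistic exposure is nearer 30%. The documents also do not name the method behind Table 22; the lower bound fits it, while independence misses the last two columns.

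The sensitivity reading fails on the plan's own table: an assumed effect cannot lose power as it grows. The 50% was placed in the null when the trial was sized. The planned CI would allow the check, but no rule ties it to 50%.

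**Conclusion.** The concern holds. The trial is sized for H0: ratio ≥ 0.50 and analysed with H0: ratio ≥ 1. The stated 94%, 96% and 98% are not the power of the planned test, which exceeds 99.99% for every endpoint at the planning ratios. Significance on the written test needs observed reductions of 11 to 22%, against 56 to 61% to establish the criterion.

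These sizes treat the planning CVs as the residual SD of a two-group comparison; the documents do not say whether they are baseline-adjusted. If the ANCOVA has a smaller residual SD, the reductions needed on the written test are smaller still. Total NNAL is taken at exactly 50% retention; with all 80 retained, its critical reduction is about 19% and its power against 0.50 is 99.7%. The 54% joint figure assumes independent endpoints; positive correlation would raise it. The mismatch itself depends on none of these assumptions.

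**What to change.** Decide which claim is intended and make hypothesis, criterion and power agree.

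- **To keep the 50% criterion:** in Protocol 12.4.4 and SAP 12.5.1.2, state H0: m1/m2 ≥ 0.50 against H1: m1/m2 < 0.50 for all five primary endpoints. Success is then the upper limit of the two-sided 95% CI for the CHTP 1.2:CC ratio below 0.50 (lower limit of the reduction above 50%) on every one. The test-wise powers then stand at N = 120, and so does the joint power, provided Protocol 12.2 and SAP 8 name the method used to combine the endpoints.
- **To keep H0: m1 ≥ m2:** remove the 50% evaluation criterion from Protocol 12.4.1, SAP 5.4.2 and the Protocol synopsis, and restate Protocol Tables 22 and 23 and SAP Tables 10 and 11 as power for a ratio below 1.

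The first option changes wording only: the CI is already planned for Table 15.2.3.1, and no new data or subjects are needed. Its price is a higher bar, the one the study was sized to clear. SAP 3 allows SAP amendments up to database lock, and the change should be recorded in SAP 9.
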